## **2.3 EVALUATION OF PROCEDURES OF THE STUDY**

### **A. Metabolic evaluation of lipodystrophic patients with NASH or NAFLD (tests will be conducted after a 10 hour fast, will be done at each visit).**

1. Blood Chemistry: The following tests will be performed after an overnight fast: fasting glucose and insulin, fasting triglyceride levels, hemoglobin A1c, fasting free fatty acid levels, fasting total, HDL and LDL cholesterol, serum ALT, AST, albumin, alkaline phosphatase, bilirubin (direct and indirect), serum electrolytes, BUN and creatinine, calcium. The previously listed blood chemistry tests will be charged to the patient's insurance as standard, routine care procedures. Approximately 10cc of serum will be aliquoted and frozen for potential future tests.

2. Determination of insulin sensitivity using HOMA-IR: The homeostatic model assessment (HOMA) will be used as a surrogate estimate of insulin resistance based on fasting insulin and glucose concentrations and calculated as fasting insulin concentration (mU/L) x fasting glucose concentration (mmol/L)/22.5 (5).

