### **Exploratory outcomes:**

We will measure change in liver function tests, alanine aminotransferase (ALT) and aspartate aminotransferase (AST). We will also explore body weight, body composition, free fatty acid levels, and HOMA-IR.

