## 2.2 INCLUSION AND EXCLUSION CRITERIA

### *Inclusion criteria for initial phase of the study:*

- Previously completed study protocol:
  - CLINICAL PROTOCOL to investigate the efficacy of recombinant human leptin (METRELEPTIN) in nonalcoholic steatohepatitis (NASH) or nonalcoholic fatty liver disease (NAFLD) associated with lipodystrophy, MB002-014 (IRMBED: HUM00058708)
- Demonstrates clinical benefit as defined by meeting at least one of the following criteria upon completion of the above stated protocols:
  - Reduction of HbA1c  $\geq$  1.0% or,
  - Reduction of triglycerides  $\geq$  30% of baseline or,
  - Decrease in insulin requirements  $\geq$  40% or,
  - Reduction in total NASH score by  $\geq$  2 points,
  - Significant worsening of metabolic parameters after discontinuation of Metreleptin if discontinuation has been undertaken.
  - A health condition that appears to have significantly improved by metreleptin for which two independent health care providers make a request to prevent drug discontinuation. In addition, the PI has to document absence of contraindications for drug continuation (such as bone marrow suppression).
- Is male or female  $\geq$  5 years old at baseline.
- Is male, female not of childbearing potential, or meets all the following criteria if female of childbearing potential (including perimenopausal women who have had a menstrual period within one year):
  - Not breastfeeding
  - Negative pregnancy test result (human chorionic gonadotropin, beta subunit [ $\beta$ hCG]) at baseline (not applicable to hysterectomized females).
  - Must practice and be willing to continue to practice appropriate birth control (defined as a method which results in a low failure rate when use consistently and correctly, such as implants, injectables, oral contraceptives, some intrauterine contraceptive devices, sexual abstinence, tubal ligation, or a vasectomized partner) during the entire duration of metreleptin treatment.
- Has physician-confirmed lipodystrophy as defined by evidence of partial (limbs) loss of body fat outside the range of normal variation.
- If  $\geq$  18 years of age, is able to read, understand and sign the U of M IRBMED approved informed consent form (ICF), communicate with study physician and study team, understand and comply with protocol requirements.

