*Treatment:* Up to fifteen patients will be enrolled into this long-term treatment extension study. Patients will be continued on metreleptin treatment as mentioned. This will be injected subcutaneously after reconstitution once a day in the morning at approximately the same time of the day that fits the subject's calendar. Dose may be titrated up to 15 mg daily based on metabolic response as needed.

*Follow-up schedule and monitoring:* Scheduled outpatient visits will occur at 6 month intervals. Tolerability will be assessed at each visit. During each visit, patients', weights, BMI, injection site inspection and basic laboratory data (comprehensive metabolic panel (fasting glucose, BUN, creatinine, sodium, potassium, chloride, CO2, calcium, total protein, albumin, total bilirubin, AST, ALT, alkaline phosphatase), fasting insulin, fasting leptin levels, fasting lipid panel (total cholesterol, triglycerides, HDL, LDL)), will be recorded. Throughout the study, lab work for CBC with differential count and creatinine kinase will be obtained at each visit.

Unscheduled visits may occur at more frequently than ever six months in order to follow-up on any adverse event or unanticipated health issues participants may be having.

*Study Termination:* Patient participation will be concluded five years after the patient's baseline appointment. At this time normal follow-up study procedures will be conducted, final drug accountability will be performed and patient will be transitioned to clinical care.

*Preparation for study visits:* Subjects will be asked to refrain from alcohol or tobacco use for 72 hours prior to the visit. They will report to the Research Center after 10 hours of fasting. They will be allowed to consume water overnight prior to the studies.

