### **4.2 RISKS ASSOCIATED WITH TREATMENT WITH RECOMBINANT HUMAN LEPTIN**

General: Hypoglycemia was the most frequent treatment-emergent adverse event reported in two previous clinical studies in 29 subjects with lipodystrophy. Metreleptin has been shown to have an antidiabetic effect in lipodystrophic patients. The investigators will monitor subjects with diabetes and consider adjustments to

antidiabetic medications (including insulin), based on the degree of glucose control achieved with the addition of metreleptin to pre-existing diabetic therapy.

In clinical weight loss studies investigating the use of metreleptin in obese patients, injection site reactions were the most common adverse event (erythema, pruritus, inflammation, urticaria and edema). All sites of injection (abdomen, arm and leg) used for the site of injection were affected. Other adverse events mentioned in the Investigator's Brochure are headache, fatigue and flu-like symptoms, weight loss, alopecia and nausea. All these effects occurred with no relationship to dosing.

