## APPENDIX

Protocol Table 1: Schedule of Study Procedures			
Studies	Baseline	Follow up visits (occurring at six month intervals)	Unscheduled visit***
Fasting biochemistry	X	X	X
Fasting adipocytokines	X	X	X
Fasting appetite regulators	X	X	X
Leptin sampling	X	X	X
Metabolomics sample	X	X	X
HOMA-IR	X	X	X
Weight, Height, and Vitals	X	X	X
Study medication distribution and accountability	X	X	X
Leptin (mg/kg/day)	5.0 – 10.0 mg/day	5.0 – 10.0 mg/day	5.0 – 10.0 mg/day
***Study procedures may be omitted at investigator's discretion during unscheduled visits.

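### Body composition is a named exploratory outcome that nothing measures, and HOMA-IR cannot be read as insulin resistance in patients who inject insulin

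*Protocol*

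**What the plan says.** Under the exploratory outcomes in section 1, after liver enzymes, the protocol states: "We will also explore body weight, body composition, free fatty acid levels, and HOMA-IR".

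**Body composition.** The follow-up paragraph in section 2.2 sets out what is recorded: "During each visit, patients', weights, BMI, injection site inspection and basic laboratory data", followed by a list of blood tests. Section 2.3 covers blood chemistry, HOMA-IR and stored research samples. The only body-measurement row in Table 1 of the Appendix is "Weight, Height, and Vitals".

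**HOMA-IR.** Section 2.3 (A.2) says the index is "used as a surrogate estimate of insulin resistance based on fasting insulin and glucose concentrations" and gives the usual product of the two divided by 22.5. It is scheduled at baseline and every six-monthly visit, with no restriction on who contributes.

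**Insulin users.** One of the alternative entry criteria in section 2.2 is "Decrease in insulin requirements" of at least 40%. Section 4.2 says investigators will monitor patients with diabetes and consider changes to "antidiabetic medications (including insulin), based on the degree of glucose control achieved". Visit preparation in section 2.2 says "They will report to the Research Center after 10 hours of fasting" and restricts alcohol and tobacco, but does not mention insulin. Neither the visit list nor Table 1 has an item for insulin use or dose.

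**The concern.** There are two separate problems.

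First, an outcome is promised for which the protocol schedules no measurement. An analysis plan cannot repair this, because it cannot analyse data that were never collected.

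Second, HOMA-IR takes measured fasting insulin as a reflection of the patient's own secretion in response to glucose. In a patient who injects insulin, the measured value can contain injected insulin, so the index depends partly on the prescribed dose. With at most 15 patients, a few insulin users whose dose changes over five years could drive the overall HOMA-IR summary. That summary might then be reported as a change in insulin resistance, or as stable resistance, when the data cannot tell which.

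**Working it through.** **Body composition: the places where a measurement could stand**

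| Place in protocol | Body measurements listed |
|---|---|
| Section 2.2, follow-up schedule | weight, BMI |
| Section 2.3, parts A and B | none (blood tests, HOMA-IR, stored samples) |
| Section 4.1, risks of evaluation methods | none (blood draws and visit time only, no imaging) |
| Appendix, Table 1 | weight, height, vitals |

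The reference list includes validation papers for MRI and DEXA, but no described procedure uses either method. A stretch of section 4.2 was not available; it concerns drug risks, so it is an unlikely place for an outcome measurement. A related slip: the HOMA-IR formula cites reference 5, which is the DEXA paper, while the HOMA paper is reference 6.

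**HOMA-IR: how far it can follow insulin dose**

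The protocol states no figure to reproduce. Its formula is HOMA-IR = I x G / 22.5, with insulin I in mU/L and glucose G in mmol/L. As a unit check, 5 x 4.5 / 22.5 = 1.0.

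Input from the protocol: a 40% reduction in insulin, the size named in the entry criterion.

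Assumptions, since the documents give none of these:
- f, the share of circulating fasting insulin that is injected;
- x, the share of injected insulin that the assay detects;
- total fasting insulin of 30 mU/L and glucose of 8 mmol/L, for illustration;
- injected insulin in the sample falls in proportion to the dose;
- own secretion and glucose stay fixed.

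Measured insulin is 30 x (1 - f + x f) before the cut and 30 x (1 - f + 0.6 x f) after it. The relative change in HOMA-IR is therefore

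-0.4 x f / (1 - f + x f),

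which does not depend on the chosen insulin and glucose levels.

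| Injected share f | Full detection (x = 1) | Half detection (x = 0.5) | No detection (x = 0) |
|---|---|---|---|
| 0 | 0% | 0% | 0% |
| 0.25 | -10.0% | -5.7% | 0% |
| 0.50 | -20.0% | -13.3% | 0% |
| 0.75 | -30.0% | -24.0% | 0% |
| 1 | -40.0% | -40.0% | not defined (measured insulin is zero) |

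Worked line for f = 0.5, x = 1: before, 30 x 8 / 22.5 = 10.67; after, (15 + 0.6 x 15) x 8 / 22.5 = 24 x 8 / 22.5 = 8.53; change -20%.

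With no detection the index does not follow the dose, but it omits the injected insulin and reads low: at f = 0.5 it is 15 x 8 / 22.5 = 5.33 instead of 10.67.

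**Releasing the fixed-glucose assumption.** In the same f = 0.5, x = 1 case, if glucose rises from 8 to 10 mmol/L after the cut, HOMA-IR is 24 x 10 / 22.5 = 10.67, which is no change.

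**The case against.** The body-composition gap has no real defence. The arguments on the other side concern HOMA-IR.

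- **It can be computed.** A reader might infer that HOMA-IR cannot be delivered at all. The documents do not support that: fasting insulin and glucose are taken at each visit, the formula is given, and the index keeps its usual meaning in patients not on insulin. The problem is interpretation in a subset. This objection stands.
- **A fall at fixed glucose is not proof of unchanged resistance.** A reader might take the -20% line to mean that HOMA-IR drops while resistance stays the same. But a patient who holds the same glucose on less insulin would ordinarily be judged more sensitive, and if resistance were unchanged glucose should rise and offset the fall. This also stands. The calculation shows only that the index responds to dose and that its movement cannot be attributed.
- **The number of insulin users is unknown.** The insulin criterion is one of several alternatives and looks back to the parent study. The remark on adjusting insulin in section 4.2 refers to adding metreleptin to existing therapy, whereas these patients already take it. This limits how large the effect can be said to be. It does not remove the point: insulin users are eligible, and nothing holds insulin constant over five years.
- **The analysis plan may handle it.** A plan not shown could separate insulin users, but it would need insulin use by visit. The protocol's visit list and schedule contain no such item, although a case report form not shown might.

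**Conclusion.** Body composition is named as an outcome and is not measured anywhere in the described procedures or schedule. This is a plain internal inconsistency and rests on no assumption.

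In insulin-treated patients, a change in HOMA-IR cannot be read as a change in insulin resistance. The possible effect of a 40% dose cut spans 0% to -40% at full assay detection, with glucose and own secretion fixed. It is smaller at partial detection for injected shares strictly between 0 and 1, and it vanishes if glucose rises enough. The injected share, the assay's detection, the glucose response and the number of insulin users are all absent from the documents, so no single figure can be defended.

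Severity is minor. A reader might infer that the efficacy conclusions are at risk, but both measures are exploratory, and the primary (triglycerides) and secondary (HbA1c) outcomes use neither of them.

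**What to change.** 1. **Section 1:** delete body composition from the exploratory outcomes. BMI may be reported in its own right, but it does not measure composition and should not be presented as a replacement.
2. **Section 2.2 and Table 1:** record insulin use and total daily insulin dose at each visit.
3. **Section 2.3 (A.2):** keep HOMA-IR at all visits, but summarise it separately by insulin use. Interpret it as insulin resistance only in patients not on insulin, for example those off insulin throughout. For insulin users, report dose in units/kg alongside it.
4. **Section 2.3 (A.2):** correct the citation for the HOMA formula from reference 5 to reference 6.

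Simply dropping visits on insulin would be a poorer choice. Patients who start insulin because control worsens would leave the summary at that point, and the trend would look better than it is. Showing both groups keeps these patients visible. The group off insulin throughout is itself selected on what happens during follow-up, so its summary should be presented as descriptive.

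The cost is one extra data field, a few lines of text, and smaller HOMA-IR groups in a study of at most 15 patients.

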## B. Research sample

We will also collect and store samples for determination of TNF- $\alpha$  soluble receptor, TGF-B, FGF-21 and other potential markers.

## 2.4 EXPECTED RESULTS

We anticipate collecting safety and efficacy data for long-term treatment of patients with partial forms of lipodystrophy.

## 3. STUDY DRUG:

*Other Names:* MyaLept (Recombinant-methionyl Human Leptin (r-metHuLeptin) METRELEPTIN)

### 3.1 STORAGE CONDITIONS AND STABILITY

The study drug will be stored in a secure location under controlled conditions at the study site or pharmacy before dispensing to subjects. Metreleptin will be stored at 2-8° C prior to reconstitution. It is recommended that the refrigerator be connected to a back-up power source, and a temperature alert system. **Amryt** will be notified if any test material is exposed to excessive or uncontrolled temperatures; possible replacement of the affected material will be considered. Study staff and subjects will be instructed in proper storage of the study drug.

### 3.2 EXPIRATION DATING

As per standard practice for experimental biologic pharmaceuticals, Amryt Pharma will conduct periodic stability assays to monitor product stability and determine appropriate expiration dating of the study drug. The appropriate **Amryt** representative shall communicate this information to the investigator.

**Amryt representative: [name]**

**Sr. Supply Chain Manager**

**Amryt Pharma PLC**

**[contact]**

### 3.3 DRUG DOSAGE AND ADMINISTRATION

Metreleptin will be administered by subcutaneous injection at the doses specified above. Subjects will be instructed by study personnel to reconstitute the medication and self-administer the injections and will perform the first injection under the supervision of study personnel.

The dosing recommendations for Metreleptin are listed below:

Body Weight	Gender	Daily Recommended Metreleptin Dose
≤40 kg	Male	0.06 mg/kg
	Female	
>40 kg	Male	2.5 mg (0.5 mL)
	Female	5.0 mg (1.0 mL)

Initial Metreleptin dose may be adjusted based upon the subject's dose at termination of the two previous studies for reasons of efficacy. Metreleptin dose may be adjusted at investigator's discretion based on clinical response (e.g. inadequate metabolic control or excessive weight loss or tolerability issues). Injections at a single site will have a maximum allowable volume of 2.0 ml. Preferably study medication will be administered at approximately the same time each day. Drug administration will occur once a day (QD). Metreleptin administration may be changed to twice a day (BID) at investigator's discretion based on clinical response (e.g. inadequate metabolic

control, tolerability issues). Dose exceeding 1.0 mL may be administered as two separate injections in order to minimize patient discomfort due to injection volume. Metreleptin dose can be injected into the abdomen, upper arm or thigh region depending on patient preference and comfort. The site(s) of injection will not occur on the limb from which subsequent blood draws will occur that day.

### **3.4 STUDY DRUG PREPARATION**

Each single use 5 mL vial of lyophilized Metreleptin (11.3 mg/vial) will be reconstituted with either bacteriostatic or sterile water immediately prior to injection. To reconstitute, 2.2 mL of either bacteriostatic or sterile water will be injected slowly down the inside wall of the vial using a syringe and needle. The vial should be inverted and gently swirled until the powder is completely dissolved. The vial is not to be shaken vigorously. The solution of reconstituted Metreleptin should be clear, colorless, and free of any floating particles. The mixed vial can be used for a maximum of three days or until sufficient volume is left for another full dose. As lyophilized Metreleptin contains no preservative, vials are designed for single use only. Latex-free syringes will be used for all procedures with the study drug. Once the vial has been reconstituted, the drug will be administered immediately (no more than 3 hours after reconstitution), as is our current practice. In the lifetime of the study, the manufacturer has conducted studies that indicate safety of use up to 3 days. Given that minimal amounts are left in the vial in our patients and that we had originally instructed them not to reuse the vials, we have been continuing this practice. Before injection, study medication will be allowed to reach room temperature (15 to 30°C). Any solution remaining in the vial can be used for a maximum of three days after reconstitution. Subjects will return all vials to study personnel at the next study visit.

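### Section 3.4 sets two incompatible in-use rules for a reconstituted vial: single use within 3 hours, and reuse for up to three days

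*Protocol*

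**What the plan says.** All of the conflicting text is in one paragraph of the protocol, Section 3.4 (Study Drug Preparation). In order, it says:

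- "Each single use 5 mL vial of lyophilized Metreleptin (11.3 mg/vial) will be reconstituted with either bacteriostatic or sterile water immediately prior to injection".
- "The mixed vial can be used for a maximum of three days or until sufficient volume is left for another full dose".
- The paragraph then turns back to the stricter rule and gives its reason: "As lyophilized Metreleptin contains no preservative, vials are designed for single use only".
- Once the vial is mixed, "the drug will be administered immediately (no more than 3 hours after reconstitution), as is our current practice".
- During the life of the study, "the manufacturer has conducted studies that indicate safety of use up to 3 days".
- Because little is left in the vial in the site's patients, and because "we had originally instructed them not to reuse the vials, we have been continuing this practice".
- Near the end of the paragraph: "Any solution remaining in the vial can be used for a maximum of three days after reconstitution".

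Section 3.1 gives a storage temperature only for the unmixed product: "Metreleptin will be stored at 2-8° C prior to reconstitution". No storage condition is stated for a vial kept after mixing.

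**The concern.** A vial cannot be both single use within 3 hours and usable for three days. The paragraph gives a reason for the stricter rule (no preservative) and then, without withdrawing that reason, gives permission to do the opposite.

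Patients reconstitute the drug and inject themselves (Section 3.3). Scheduled visits are six months apart and participation lasts five years (Section 2.2, Follow-up schedule and Study Termination). Only the first injection is stated to be supervised. Staff who write or deliver the handling instructions could take either rule from this text. The same act, drawing a second dose from yesterday's vial, would be a deviation under one sentence and allowed under another. What is at stake is safe and uniform drug handling.

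**Working it through.** The protocol states no figure to reproduce. The check has two parts: whether the text settles on one rule, and whether the two rules lead to different actions.

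**1. Does the text settle on one rule?**

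| Rule | Where in the Section 3.4 paragraph | Condition attached |
|---|---|---|
| Three days | second in-use statement | mentions volume for another full dose; none on diluent or storage |
| Single use | opening, and again after the first three-day sentence | reason: no preservative |
| Within 3 hours | after the single-use sentence | labelled current practice |
| No reuse continues | after the mention of manufacturer studies | reason: little is left |
| Three days | last in-use statement | none |

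If the paragraph ended at the fourth row, the three days could be read as background and the 3 hours as the rule. The fifth row comes after that explanation and restores the permission, so the paragraph does not end on a single rule.

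**2. Do the rules lead to different actions?**

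Inputs: 2.2 mL of diluent and 11.3 mg per vial (Section 3.4); 2.5 mg = 0.5 mL, 5.0 mg = 1.0 mL, and 0.06 mg/kg at 40 kg or less (Section 3.3); titration up to 10 mg daily (Section 2.2, Restorative leptin therapy) or 15 mg daily (Section 2.2, Treatment); 5.0 to 10.0 mg/day (Appendix, Protocol Table 1).

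Concentration: 2.5 mg / 0.5 mL = 5 mg/mL. The vial content agrees: 11.3 / 2.2 = 5.14 mg/mL.

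Volume left = 2.2 mL − dose volume. Further full doses = volume left / dose volume, rounded down.

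| Single dose | Dose volume | Left in vial | Share left | Further full doses |
|---|---|---|---|---|
| 2.4 mg (40 kg × 0.06 mg/kg) | 0.48 mL | 1.72 mL | 78% | 3 |
| 2.5 mg | 0.5 mL | 1.7 mL | 77% | 3 |
| 5 mg | 1.0 mL | 1.2 mL | 55% | 1 |
| 10 mg | 2.0 mL | 0.2 mL | 9% | 0 |

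Patients under 40 kg use less than 0.48 mL, so more than 1.72 mL remains.

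At every dose in the Section 3.3 table, the three-day rule allows at least one more full injection from the vial and the single-use rule forbids it. Little is left only near 10 mg given as one injection.

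Twice-daily dosing, which Section 3.3 allows, gives the same contrast. At 5 mg twice daily, 2 × 1.0 = 2.0 mL fits in one vial under the three-day rule. Doses many hours apart need two vials a day under the 3-hour rule.

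For larger doses, the last three-day sentence covers any remainder and does not require it to make a full dose. At 10 mg the 0.2 mL left is covered. At 15 mg (15 / 5 = 3.0 mL, so two vials) the 4.4 − 3.0 = 1.4 mL left is also covered. Read literally, that sentence conflicts with single use at every dose that leaves any solution.

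**The case against.** The best defence is that the paragraph does identify the working rule. The 3-hour statement is mandatory and labelled current practice, the no-reuse instruction is said to continue, and the three-day sentences only permit. On that reading three days is an outer limit, the site works inside it, and the last sentence is merely misplaced. The study has at most 15 patients, who come from the parent metreleptin study. Staff train them, and all vials are returned at the next visit. Patients may also be on doses above the Section 3.3 table. The protocol says little is left in their vials, and the Appendix range runs to 10 mg/day.

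Much of this stands. It shows which rule the site probably follows, and it limits how far the problem reaches. It does not remove the conflict. A permission to reuse for three days cannot sit inside a statement that vials are for single use only, and the permission is repeated after the explanation.

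A reader might infer any of three further points, none of which the document supports:

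- **That patients are reusing vials or being harmed.** The stated instruction was not to reuse, nothing shows that any patient was given the three-day rule, and the manufacturer's studies may support it.
- **That allowing both diluents under one time limit is a separate error.** The protocol does not say which diluent those studies covered, so the right limit for each cannot be judged here. Diluent matters only as a condition if three-day use is kept.
- **That the rules stop differing above 1.1 mL (2.2 / 2, or 5.5 mg), where a second full dose no longer fits.** Only the first three-day sentence refers to a full dose; the last one does not.

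**Conclusion.** The point holds as an internal contradiction in current operative text. Section 3.4 states two incompatible in-use rules and does not finally choose between them. At the Section 3.3 doses the difference is practical: 1.2 mL to 1.72 mL or more of a 2.2 mL vial remains, enough for one to three further full doses or more at low body weight. This rests on the nominal 5 mg/mL implied by Section 3.3 and ignores losses in drawing up.

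Actual patient doses are not given, so the number affected is unknown and could be small. Harm from reuse is neither shown nor excluded. Sample size, power and error rates are unaffected. It should be corrected because it concerns handling of a self-injected drug and is cheap to fix.

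**What to change.** Keep one rule in Section 3.4.

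- **Default:** keep the stated practice. Each vial is for a single use, injected within 3 hours of mixing, and any remainder is not used. Delete both three-day sentences.
- **Alternative, if three-day use is intended:** limit it to the diluent or diluents covered by the manufacturer's data, state the storage condition after mixing that those data support, and delete the single-use and 3-hour wording for that case.

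Either way, give patients the same rule in their instructions.

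The cost is revised protocol and patient wording. Under the default, extra vials are needed only for a patient who now reuses them. On 5 mg once daily that means going from one vial per two days (2 × 1.0 = 2.0 mL) to one per day. On 2.5 mg it means going from about one per three days (3 × 0.5 = 1.5 mL) to one per day. Where the no-reuse practice is already followed, no extra drug is needed.
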